1.1 Background and rationale

The management of acute Achilles tendon ruptures has been the subject of a long-standing debate. Contemporary rehabilitation protocols emphasizing early weight bearing and mobilization have furthermore blurred differences in treatment results. Open repair (OR) may reduce the risk of re-rupture, but at the expense of surgical complications such as delay in wound-healing and infection. This has led to the development of percutaneous and minimal invasive surgical techniques (MIS). The demonstration of significant differences comparing OR, MIS and conservative treatment (CT), requires a large sample, and although the previously reported differences have lacked statistical significance, they may be of substantial clinical value. We have therefore conducted a three-arm RCT comparing CT, OR and MIS that is sufficiently large to be able to demonstrate significant differences.

1.2 Trial Objectives

1.2.1 Primary Objective

The primary objective is to assess if one of the three treatments is superior to at least one of the others measured by the Achilles tendon Total Rupture Score (ATRS) [2, 3] score at 1-2 years post rupture.

1.2.2 Secondary Objectives

The secondary objectives of this study are to assess if there are differences between the three treatment groups with regards to

- The ATRS at 3 and 6 months.
- The Short form 36 health survey (SF-36) [4, 5] at 6 months and 1-2 years.
- The physical test results in the Muscledab Measurement system [6] at 6 months and 1-2 years.
- Re-rupture rate between the three treatment groups at 1 year.

2 Trial Methods

2.1 Trial Design

The Achilles study is designed as a randomized, controlled, multicentre, single-country, comparative study.

2.2 Randomisation

Eligible patients were allocated in a 1:1:1 ratio between CT, OR and MIS. Treatment allocation was done by block randomization, stratified by hospital, with 6, 9 or 12 patients in each block. Details of allocation sequence generation was provided in a separate document unavailable to those who enrolled patients or assigned treatment.

2.3 Sample size

The sample size was based on the primary endpoint of ATRS at 1-2 years. The calculation was based on a one-way ANOVA analysis, assuming a standard deviation of 20 in each treatment group. A total sample size (study completers) of 480 (160 in each group) was deemed necessary to achieve 80%

STATISTICAL ANALYSIS PLAN for the Achilles trial

power to detect a difference of ATRS of 7 between the groups in two-sided tests at 5% significance level. To compensate for withdrawals/loss to follow-up, a total enrolment of 530 patients was targeted.

2.4 Statistical Framework

2.4.1 Hypothesis Test

This trial will employ a hierarchical testing procedure as follows:

1. First, a test of overall effect of treatment at 1-2 years is performed. The null hypothesis is that there is no difference in the change in ATRS score from baseline to 1-2 years between the three study arms. The alternative hypothesis is that there is a difference between at least two of the three treatment arms. The test will be performed at the (two sided) 5% significance level.
2. If the overall test shows that there is a significant difference on the 5% level, then tests of a difference in the change from baseline to 1-2 years ATRS score will be performed pairwise between the treatment arms. The null hypotheses in these tests will be that there is no difference between the treatment arms. The alternative hypotheses are that there is a difference between the two treatment arms being compared. These tests will be performed at the (two sided) 5% significance level.

The hierarchical testing procedure abides by the closed testing procedure, allowing a 5% significance level to be used in each test, while at the same time maintaining a family-wise error rate at 5%.

All other tests than described in step 1 and 2 above, will be regarded as supportive or exploratory.

Note that if the test in step 1 shows that there is no significant difference between treatment groups, a pairwise comparison between treatment groups will still be reported, but these are to be considered as secondary analyses.

2.4.2 Decision Rule

This protocol is designed to address a single primary endpoint, in a hierarchical fashion as described above. A difference in the effect of the treatment arms will be claimed if null hypothesis in step 1 of the hierarchical testing procedure outlined in Section 2.4.1 is rejected. That is, the two-sided p-value is less than 5%.

If step one of the testing procedure in step 1 in Section 2.4.1 shows significance, then tests outlined in step 2 of Section 2.4.1 will be performed.

1. Superiority of the OR group over the MIS group will be claimed if the two-sided p-value in the test comparing the change from baseline to 1-2 years ATRS score is less than 5%, and if the effect goes in favour of the OR group. Superiority of the MIS group will be claimed if the effect goes in favour of this group.
2. Superiority of the OR group over the CT group will be claimed if the two-sided p-value in the test comparing the change from baseline to 1-2 years ATRS score is less than 5%, and if the

STATISTICAL ANALYSIS PLAN for the Achilles trial

effect goes in favour of the OR group. Superiority of the CT group will be claimed if the effect goes in favour of this group.

3. Superiority of the MIS group over the CT group will be claimed if the two-sided p-value in the test comparing the change from baseline to 1-2 years ATRS score is less than 5%, and if the effect goes in favour of the MIS group. Superiority of the CT group will be claimed if the effect goes in favour of this group.

2.5 Statistical Interim Analyses and Stopping Guidance

There will be no interim analyses in this trial.

2.6 Timing of Final Analysis

The main analysis is planned when all patients have concluded a minimum of 334 days of follow up, all data up to two years have been entered, verified and validated and the primary database has been locked.

2.7 Timing of Outcome Assessments

For all clinically planned measures, visits should occur within a window of the scheduled visit. Visits outside visit window is regarded a protocol deviation. The target day and visits window are defined in the protocol as:

Visit Label	Target Day	Definition (Day window)
Diagnosis	-1	Prior to Day 0
V1. Baseline	Day 0 (Randomization)	Day 0
V2. Surgery/Casting	Day 1	< 8 days from injury
V2. 2 weeks	14 days from casting	Target day \pm 7 days
V3. 4 weeks	28 days from casting	Target day \pm 7 days
V4. 8 weeks	56 days from casting	Target day \pm 14 days
V5. 3 months	91 days from casting	Target day \pm 30 days
V6. 6 months	182 days from casting	Target day \pm 30 days
Last study visit*	364 days from casting	334 to 728

*The patients are physically tested by a physiotherapist at 1-2 years. Most often they are asked to complete the PROMs prior to the testing, either by link send by e-mail, on site on a tablet, or on paper when a tablet is not present or online. Some patients did not show up for the 1-2 years testing but did complete the PROMs. Some patients showed up for testing at 1-2 years but did not complete the questionnaires. The last study visit is defined as the last of either the 1-2 years test day or completion of the 1-2 years PROMs.

STATISTICAL ANALYSIS PLAN for the Achilles trial

For analysis and tabulation purposes, we define study time points as

Time Point Label	Target Day	Definition (Day window)
TP1. Baseline	Day 0 (Randomisation)	Information up to randomisation + 14 days
TP2. Month 3	91	Days 61 to 121
TP3. Month 6	182	Days 151 to 212
TP4. Year 1-2	364	Days 334 to 728

3 Statistical Principles

3.1 Confidence Intervals and p-values

All calculated p-values will be two-sided and compared to a 5% significance level. If a p-value is less than 0.05, the null hypothesis in the test will be discarded. Efficacy estimates for the comparison of specific treatment arms will be presented with two-sided 95% confidence intervals. This trial utilizes a hierarchical testing procedure for the primary endpoint (see Section 2.4.1), which maintains the type I error rate at 5%.

3.2 Adherence and Protocol Deviations

3.2.1 Adherence to Allocated Treatment

The number and proportion of patients that received the intervention they were randomized to will be presented.

3.2.2 Protocol Deviations

The following are pre-defined major protocol deviations regarded to affect the efficacy of the intervention:

- Entering the trial when the eligibility criteria should have prevented trial entry
 - Lack of sufficient skills in Norwegian language to understand the questionnaires.
 - Outside the age criteria (18-60 years).
 - Misdiagnosed.
 - Earlier injury to one of the Achilles tendons.
- Received other intervention than allocated to.
- Lack of technical competence for randomized surgical method.

The number (and percentage) of patients with major protocol deviations will be summarised by treatment group with details of type of deviation provided. All randomized patients will be used as the denominator to calculate the percentages. No formal statistical testing will be undertaken.

3.3 Analysis Populations

We define the following patient population in this trial.

- **All randomized patients:** All patients that have been randomized regardless if they actually received treatment or not.
- **Full analysis set (FAS):** All patients that are randomized, received treatment, and where ATRS was measured at least once post baseline (i.e. at 3 months, 6 months or 1-2 years). Patients are allocated to the treatment they were randomized to.
- **Per protocol set (PPS):** Similar to the FAS, but patients are allocated to the treatment they actually received.
- **Complete Case set (CCS):** The subset of patients in the FAS that has ATRS measurements at all follow-up visits. Patients are allocated to the treatment they were randomized to.

The FAS will be used for the primary analysis, while the PPS and the CCS will be used for sensitivity analyses.

4 Trial Population

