4.2 Withdrawal/Follow-up

The status of eligible and randomised patients at trial end will be tabulated by treatment group according to whether they

- completed intervention, but not assessments.
- completed assessments, but not intervention.
- withdrew consent.
- lost to follow-up.

STATISTICAL ANALYSIS PLAN for the Achilles trial

- excluded due to delay from injury to surgery (>7 days).
- excluded due to protocol deviations after randomisation but occurring prior to surgery.
- Unable to measure the primary endpoint due to:
 - comorbidity that compromise rehabilitation or testing.
 - death during follow up.
 - re-rupture on the contralateral side during follow up.
 - other surgery on the lower extremities during follow up.

Time from randomisation to treatment discontinuation and time from randomisation to withdrawal/lost to follow-up will be presented graphically using a CONSORT flow diagram.

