5.2 Analysis Methods

5.2.1 Primary Outcome

5.2.1.1 Primary Analysis

The primary outcome in this trial is the change in the ATRS score from baseline to the 1-2 years visit.

The primary analysis will be performed by applying a linear mixed effects model to model the longitudinal change from baseline ATRS measurements at the 3-month, 6-month and 1-2-year visits. A fixed interaction term between the follow-up visit and treatment group will be included in the model. The baseline ATRS measurement will be included as a fixed covariate in the model. Study centre, which was used as a stratification variable in the randomization, will also be included as a fixed covariate. An individual-specific random intercept term will be included in the model to account for the dependencies within individuals. An unstructured correlation structure will be assumed for the repeated measurements.

From the fitted model, the estimated marginal means will be computed for each time point and each treatment. Based on the estimated marginal means, an omnibus test, where the null hypothesis is that there is no difference between the three treatment groups, will be performed for the 1-2-year visit. This corresponds to step 1 in Section 2.4.1. If the test is statistically significant on the 5% level, pairwise testing between the three treatment groups will be performed for the 1-2-year visit (step 2 in Section 2.4.1). A 5% significance level will be used in each of these tests. As described in Sections 2.4.1-2.4.2, the hierarchical testing procedure maintains the overall type I error rate at 5%. The estimated marginal means with 95% confidence intervals of the change in ATRS from baseline will be presented for each of the treatment groups for the 1-2 years visit.

If the omnibus test at the 1-2 years visit does not show statistical significance, then no further hypothesis testing will be performed. However, the estimated marginal means and the accompanying 95% confidence intervals will still be presented, but should be considered as secondary analyses.

The analysis will be conducted in the FAS.

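### The FAS requires receipt of treatment, so a randomised patient who received none of the three treatments leaves the primary analysis even if ATRS was measured (minor; free to correct)

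*SAP*

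**What the plan says.** SAP section 3.3 defines four sets.

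- All randomised patients: "All patients that have been randomized regardless if they actually received treatment or not".
- FAS: "All patients that are randomized, received treatment, and where ATRS was measured at least once post baseline". On arm assignment: "Patients are allocated to the treatment they were randomized to".
- PPS: "Similar to the FAS, but patients are allocated to the treatment they actually received".
- CCS: the FAS patients with ATRS at every follow-up visit.

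On their use, section 3.3 states "The FAS will be used for the primary analysis, while the PPS and the CCS will be used for sensitivity analyses", and section 5.2.1.1 repeats for the primary analysis: "The analysis will be conducted in the FAS". Sections 5.2.2.1, 5.2.3.1 and 5.2.4.1 place the re-rupture, SF-36 and muscle-lab analyses in the same set.

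Section 2.7 puts randomisation at Day 0 and treatment after it ("V2. Surgery/Casting Day 1 < 8 days from injury"). The status table in section 4.2 has a row for patients who "completed assessments, but not intervention". It also has rows for exclusion because surgery came more than 7 days after injury, and for exclusion because of a deviation between randomisation and surgery.

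**The concern.** Whether a patient belongs to the primary set depends on something that happens after randomisation. A randomised comparison is protected when patients are kept whatever happens to them afterwards. Removing some who have a measured outcome gives that protection up, and the harm is greatest if the removals differ by arm. Two of the three arms need an operation, and two of the exclusion rows in section 4.2 are worded around surgery, so different losses by arm are possible.

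Nothing is gained in return. By section 5.2.1.4 the mixed model can use any patient with at least one follow-up ATRS, and a missing baseline score is imputed. The SAP already accepts non-adherence by keeping crossovers in their randomised arm, so dropping only the untreated is out of line with its own as-randomised principle.

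**Working it through.** **Step 1: who is dropped.** The FAS keeps patients in their randomised arm, and the PPS regroups the same patients by treatment received. Item 4 of section 5.2.1.5 describes that regrouping for patients who received a treatment other than the allocated one. If the FAS required the allocated treatment, no such patient would be left to regroup. The condition therefore means any study treatment, and it removes only patients who received none of the three.

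**Step 2: does any analysis restore them?**

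| Planned element | Section | Includes an untreated patient with measured ATRS? |
|---|---|---|
| Primary analysis in the FAS | 5.2.1.1 | No |
| Sensitivity 1 and 2 (baseline imputation) | 5.2.1.5 | No; they vary the handling of baseline ATRS only |
| Sensitivity 3 (inverted scores) | 5.2.1.5 | No; it varies scoring only |
| Sensitivity 4 (PPS) | 3.3, 5.2.1.5 | No; same membership as the FAS |
| Sensitivity 5 (CCS) | 3.3, 5.2.1.5 | No; a subset of the FAS |
| Multiple imputation | 5.2.1.4 | No; only for patients with no follow-up ATRS, and only above 5% |
| All randomised patients | 3.2.2, 3.3 | Denominator for deviations; no efficacy analysis |

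**Step 3: size.** The SAP gives no count of untreated patients, so there is no planned figure to correct.

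Inputs from section 2.3: SD 20, target difference 7, 160 completers per arm, 530 enrolled (530/3 = about 177 per arm). As a check on these, a one-way ANOVA with means 0, 3.5 and 7 and SD 20 has noncentrality 160 × (3.5² + 0² + 3.5²)/20² = 9.8 and power 80.4% at 160 per arm. It needs 159 per arm, 477 in total, so the stated 480 is reproduced.

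Let p be the share of an arm that is dropped, and D the mean ATRS of retained patients minus that of dropped patients. The mean over everyone in the arm is (1 − p) × retained mean + p × dropped mean. The retained mean minus this equals p × D. Both p and D are assumptions:

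| p | Patients of 177 | Shift at D = 10 | Shift at D = 20 |
|---|---|---|---|
| 1% | 1.8 | 0.1 | 0.2 |
| 2% | 3.5 | 0.2 | 0.4 |
| 5% | 8.8 | 0.5 | 1.0 |

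At 2% the shift is 0.2/7 = 2.9% to 0.4/7 = 5.7% of the target difference.

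Suppose there is no true difference, the loss falls on one arm only, and each arm has 160 patients with SD 20. The 5% omnibus ANOVA then rejects 5.1% (D = 10) to 5.3% (D = 20) of the time at p = 2%, and 5.5% to about 7% at p = 5%. This uses the simple ANOVA of section 2.3 and not the planned mixed model, so it shows only the order of magnitude.

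**The case against.** The strongest reply is that hardly anyone may be affected. A patient must have received none of the three treatments and still have returned an ATRS. Section 2.7 gives all arms one surgery or casting visit and times later visits from casting, and nothing in the SAP shows that such patients exist in any number. The section 4.2 row for completed assessments without completed intervention does not prove it either: someone who began treatment and stopped has received treatment and stays in. Exclusions will also be visible, since section 4.1 reports patients left out of the primary analysis with reasons, and section 3.2.1 reports adherence. All of this stands, and it is why the point is minor. It does not supply a reason for the condition, and a count in a flow diagram is not an estimate that includes these patients.

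A reader might infer something stronger: that surgical-arm patients who decline the operation and are casted are dropped, so that the rule strips decliners from the OR and MIS arms and never touches the CT arm. The SAP does not support this. By step 1 such patients stay in their randomised arm, and an untreated CT patient would be removed just as an untreated surgical patient would. For the same reason, the shares in step 3 must not be read as rates of declining surgery.

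It may also be tempting to argue from lack of blinding or from patients backing out. The SAP describes neither. The possibility of different loss by arm rests only on the order of events in section 2.7 and the surgery-linked rows in section 4.2.

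**Conclusion.** The point holds in a narrow form. Section 3.3 conditions the primary set, and every efficacy analysis built on it, on an event after randomisation; the condition has no analytic purpose, and no sensitivity analysis recovers the patients lost. The bias is possible but probably small: 0.2 to 0.4 ATRS points at an assumed 2% of an arm and an assumed gap of 10 to 20 points. It would be zero if no untreated patient returned an ATRS. The conclusion rests on reading the condition as any study treatment, which the PPS definition and item 4 of section 5.2.1.5 imply but which the FAS definition does not spell out. The sample size is unaffected. This is a minor point and a free improvement.

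**What to change.** 1. In section 3.3, delete the words *received treatment* from the FAS definition. The set then holds all randomised patients with at least one post-baseline ATRS, analysed as randomised.
2. State that the same rule covers patients whom section 4.2 lists as excluded after randomisation and before or because of delayed surgery, if their ATRS was measured. Otherwise the deletion leaves that route out of the analysis open. This concerns the analysis set only, not how those patients are managed.
3. Report non-receipt by arm in the adherence summary of section 3.2.1.
4. If a treated-only analysis is wanted, keep it as a sensitivity analysis and say there that the term means any of the three study treatments. Say also how the PPS handles a patient who received none of them, since such a patient has no group by treatment received.

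The cost is two deleted words and a few added sentences. No new data are needed, and the only effect on the primary analysis is that a few more patients may enter it.

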4.1 Screening Data, Eligibility and Recruitment

The total number of screened patients and reasons for not entering the trial will be summarised and tabulated.

A CONSORT flow diagram (appendix A) will be used to summarise the number of patients who were:

- assessed for eligibility at injury
- eligible at injury
- eligible and randomised
- eligible but not randomised*
- received the randomised allocation
- did not receive the randomised allocation*
- lost to follow-up*
- randomised and included in the primary analysis
- randomised and excluded from the primary analysis*

*reasons will be provided.

4.2 Withdrawal/Follow-up

The status of eligible and randomised patients at trial end will be tabulated by treatment group according to whether they

- completed intervention, but not assessments.
- completed assessments, but not intervention.
- withdrew consent.
- lost to follow-up.

STATISTICAL ANALYSIS PLAN for the Achilles trial

- excluded due to delay from injury to surgery (>7 days).
- excluded due to protocol deviations after randomisation but occurring prior to surgery.
- Unable to measure the primary endpoint due to:
 - comorbidity that compromise rehabilitation or testing.
 - death during follow up.
 - re-rupture on the contralateral side during follow up.
 - other surgery on the lower extremities during follow up.

Time from randomisation to treatment discontinuation and time from randomisation to withdrawal/lost to follow-up will be presented graphically using a CONSORT flow diagram.

4.3 Baseline Patient Characteristics

The patient demographics and baseline characteristics to be summarised include study centre, age in years, gender, Body mass index (BMI), injured side (left/right), education, smoking status, ASA1/ASA2 and baseline ATRS.

Patient demographics and baseline characteristics will be summarised by randomised treatment arm and overall using descriptive statistics (N, mean, standard deviation, median) for continuous variables, and number and percentages of patients for categorical variables. Any clinical important imbalance between the treatment groups will be noted.

5 Analysis

5.1 Outcome Definitions

5.1.1 General Definitions and Derived Variables

5.1.1.1 Body Mass Index

Body Mass Index (BMI) = Body weight in kilograms divided by the square of the height in meters.

5.1.1.2 Achilles tendon Total Rupture Score

The acute Achilles tendon Total Rupture Score (ATRS) was developed in Sweden and published in 2007 (2). The ATRS is a patient reported outcome measure (PROM) designed to assess outcomes in patients with ruptures of the Achilles tendon. It contains ten questions, and each question is answered on an 11-point Likert scale ranging from 0 to 10. The total score is calculated by summing the individual Likert items. A score of 100 represents the absence of symptoms, whereas a score of 0 represents severe symptoms. The Norwegian version of the ATRS was validated, reliability tested and published in 2017/2018 (3). The Norwegian adaption of the ATRS demonstrates acceptable validity and reliability for use in the Norwegian population to assess clinical outcomes in patients with Achilles tendon ruptures.

If any of the 10 questions lacks an answer, this trial will follow the ATRS manual (8). Most importantly, if one or more of the 10 questions lacks an answer, the total ATRS score is treated as a missing value.

5.1.1.3 Short Form 36

STATISTICAL ANALYSIS PLAN for the Achilles trial

The Short Form 36 (SF-36) is a self-assessment health status questionnaire composed of 36 questions sorted into eight multi-item scales. The SF-36 also provides two summarized measures represented by the physical component summary (PCS) and the mental component summary (MCS). The validity and reliability of the Norwegian translation of SF-36 have been found to be satisfactory (4, 5).

